5. Measurement of carotid intima media thickness using a General Electric LogiQ ultrasonographic device with border detection software. A 14.2 x 47 mm lineal GE 12L-RS transducer was used. International measurement norms were used ³.
6. Measurement of liver fat infiltration using the same ultrasonographic device but with a convex multifrequency (2 – 5.5 MHz) 4C RS GE transducer. Fatty infiltration was ascertained using Hamaguchi score ⁴. We have previously validated this technique against liver fat measurement using magnetic resonance spectroscopy.

Participant features were reassessed with the new laboratory determinations and those who continued to comply with inclusion criteria were randomized into two groups, balancing by gender, age, body mass index and urine albumin excretion expressed per mg of creatinine. Randomization was carried out using an iteration software based on random number generation. The output was an individual number for each patient. This number was sent to the oil manufacturer, who had the codes for each number and prepared the supplement to be used.

1. Active supplement contained 282 mg of docosahexanoic and eicosapentanoic acids per ml.
2. Placebo supplement: Contained corn oil

Participants were instructed to drink 13 ml of the supplement per day in one or two doses. Both supplements had a lemon flavor and were indistinguishable due to deodorization technology used

to prepare them. Therefore the investigators and the participants were blinded to the treatment allocation.

The intervention period lasted 3 months. Participants were cited every two weeks to provide them with a new bottle of supplement. They returned the used bottle and the residual content was measured to determine compliance. They were also interrogated about adverse events or other eventualities.

At the sixth week and at the end of the intervention at 12 weeks, participants were subjected to the same assessments done at baseline.

All participants could call the investigators in any moment if they an intercurrent problem. If a subject failed to attend an appointment, he or she was called by phone or visited at their houses to find out the reason for not showing. If a subject declined to continue in the study, he or she was considered as a loss from follow up.

Data analysis:

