Until the end of the intervention period for all participants, they were only identified with their allocation number. Once the intervention ended, each participant was classified as pertaining to group 1 or 2, without knowing which was the group receiving the active supplement. All red cell membrane fatty acid composition measurements, was analyzed when all statistical analysis of the rest of the variables were done, to maintain the blinding. An intention to treat analysis was performed.

Normality of variable distribution was analyzed using Shapiro Wilk test. Since most variables had a non-normal distribution, results are expressed as median (interquartile range). By the same token, non-parametric statistical methods were used to compare variables. Chi square or fisher tests were used to compare proportions. Differences between groups were compared using Kruskal

Wallis test. To assess changes in repeated measures of a single parameter a mixed linear regression model for repeated measures was used⁵. Significance level was set at 0.05

The main outcome of the study was set as a reduction in urine albumin excretion by 20% or more. We anticipated that 35% more participants receiving the active product than those receiving placebo would attain this reduction. Thus, the sample size to obtain results with an α of 0.05 and a power of 0.8 was 38 participants per group.

Results:

Participant flow is shown in figure 1. We randomized 50 participants per group and lost five in corn oil group and four in Ω -3 group. The demographic features, body mass index and baseline albumin excretion of participants randomized to each group are shown in table 1. No differences between groups were observed, therefore the premises of randomization were correctly attained. Red blood cell membrane phospholipids fatty acid composition during the study are shown in table 2. Patients receiving the active supplement had significant increases in eicosapentanoic and docosahexanoic fatty acid levels.

A 20% reduction in urine albumin excretion was attained in 13 participants of group 1 and 19 participants of group 2 (fisher $p= 0.274$). The clinical and laboratory parameters in the three assessment periods for groups 1 and 2 are observed in table 3.

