Summarizing, participants receiving corn oil maintained their pulse wave velocity during the follow up while controls experienced an increase in this parameter. Triacylglycerol levels decreased significantly in the Ω -3 group and glycosylated hemoglobin increased significantly in both groups

The compliance with the study product for groups 1 and 2, calculated measuring the leftovers was 88.7 (74-97) and 89.6 (77-98) %, respectively ($p= 0.99$). Eighty nine adverse events were recorded (48 in group 1 and 27 in group 2, $p = \text{NS}$). Of these, two were severe (a severe hyperkalemia and

the discovery of a cervical mass that resulted in a medullary thyroid carcinoma, both in participants of group 1). Mild gastrointestinal symptoms were reported by 12 and 14 participants in groups 1 and 2 respectively.

Preliminary conclusions:

1. The primary outcome measure of the study was not attained, since urine albumin excretion decreased by 20% or more in a similar proportion of participants in each intervention group.
2. The striking reduction in serum triacylglycerol observed in participants receiving Ω -3 fatty acids is a known pharmacological effect of Ω -3 fatty acids.
3. The deterioration of glycosylated hemoglobin in both groups, may be associated with the fact that participants received 110 Kcal/day of extra calories with the supplement.
4. The lack of increase in pulse wave velocity in group 2 may indicate that the supplement that this group received had a favorable effect on arterial stiffness.
5. The supplement was well tolerated. The lack of differences between groups in compliance and gastrointestinal complains indicates that the fish oil effectively almost completely deodorized.

[figure not shown]
Figure 1

Table 1: Initial features of randomized participants expressed as median (interquartile range)

	Gender (F/M)	Age (years)	Body mass index (kg/m²)	Urine albumin (mg/g creatinine)
Corn oil				
Group	26/24	66 (58-74)	31 (27.2-35.3)	604.5 (212-1234)
Ω-3 group	23/27	67 (56-74)	33.5 (30-37.3)	365.5 (157-1079)
Difference		NS	NS	NS

Table 2: Changes in red blood cell membrane phospholipids fatty acid composition. Values expressed as median (interquartile range) in mg/100 mg of total fatty acids

	Corn oil group (n=45)			Ω-3 Group (n=46)			p ¹
	Basal	Six weeks	Final	Basal	Six weeks	Final	
Pentadecanoic Acid (C15:0)	0.2 (0-3)	2.3 (0-3.2)	2 (0-3)	0.2 (0-2.9)	1.2 (0-3.2)	2.3 (0-3.3)	b

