Eicosapentanoic Acid (C 20:5 n-3)	0.4 (0-0.7)	0.4 (0-0.7)	0.5 (0.2-0.8)	1.3 (0.4-3)	2.8 (1.4-3.3)	2.6 (1.1-3.5)	c
Docosadienoico Acid (C22:2)	0 (0-0)	0 (0-0)	0 (0-0)	0 (0-0)	0 (0-0)	0 (0-0)	
Docosahexanoic Acid (C22:6 n-3)	1.9 (1.3-2.8)	1.8 (1.4-2.6)	1.6 (1-2.4)	2.7 (2-3.7)	2.9 (2.2-3.8)	2.8 (2.2-4.2)	c
Total polyunsaturated	27.5 (23.4-30.8)	26.6 (24.1-30.3)	26.6 (22.4-29.9)	27.6 (23.2-31.5)	27 (24.3-31.4)	26.1 (22.1-29.9)	b

^a = significance for differences between groups determined by a mixed effects lineal regression model for repeated measures. ^b = difference between groups without intervention effect, ^c= intervention effects without differences between groups ^c= intervention effect with differences between groups (Ω -3 fatty acid effect)

Table 3: Measured parameters in both treatment groups, expressed as median (interquartile range)

	Corn oil group (n=45)			Ω-3 Group (n=46)			p [†]
	Basal	Six weeks	Final	Basal	Six weeks	Final	
Clinical parameters							
Systolic blood pressure (mm Hg)	129 (121-142)	134 (123-140)	133 (123-150)	135.5 (126-153)	137 (122-150)	138.5 (128-149)	
Diastolic blood pressure (mm Hg)	81 (73-87)	80 (73-86)	83 (74-90)	81.5 (73-95)	80.5 (75-92)	84.5 (74-93)	
Weight (kg)	76.4 (69.7-91.5)	77.4 (71.7-90.5)	77.6 (70.1-93.3)	90.4 (79.1-101.2)	91.05 (77.5-100.5)	91.2 (77.6-101.9)	
Waist circumference (cm)	104 (97-113.2)	104 (97.6-114)	105 (96-113)	110.5 (103.5-122.4)	112 (104.2-120)	111.25 (104-120.6)	
Carotid intima media thickness:							
Left (mm)	0.66 (0.6-0.83)	0.67 (0.57-0.84)	0.71 (0.58-0.83)	0.71 (0.61-0.88)	0.735 (0.62-0.85)	0.695 (0.59-0.82)	
Right (mm)	0.62 (0.55-0.715)	0.62 (0.54-0.73)	0.645 (0.555-0.755)	0.68 (0.6-0.78)	0.7 (0.61-0.78)	0.71 (0.61-0.79)	
Arterial stiffness measures							
Augmentation pressure (mm Hg)	8 (5-12)	9 (5-15)	12 (5-19)	9 (5-16)	11 (6-20)	12 (4-18)	b
Augmentation index (%)	18 (9-29)	23 (11-35)	25 (14-39)	20 (8-31)	27 (12-38)	23 (9-34)	b
Reflection magnitude (%)	66 (61-73)	70 (59-75)	69 (57-75)	67 (61-73)	67 (63-73)	66 (61-74)	
Pulse wave velocity (m/s)	9.3 (8.5-10.7)	9.7 (8.3-11)	9.7 (8.3-11.2)	9.75 (8.1-10.6)	10 (7.6-10.8)	10.1 (8-10.9)	c
Liver ultrasound							
Liver steatosis score (units)	3 (2-4)	3 (2-4)	3 (3-4)	3 (2-4)	4 (2-4)	3 (3-4)	
Laboratory values							
Fasting glucose (mg/dl)	94 (86-115)	97 (89-120)	95 (86-132)	99 (83-118)	107.5 (90-143)	103.5 (90-137)	
Total cholesterol (mg/dl)	165 (138-203)	162 (135-195)	160.5 (134-195)	170 (140-204)	167.5 (141-203)	154.5 (127-176)	

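### The primary result is described as intention to treat, but its Fisher p-value of 0.274 fits only the 91 participants not lost (13/45 vs 19/46), not the 100 randomised

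*Combined protocol and SAP*

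**What the plan says.** The Data analysis section says "An intention to treat analysis was performed", with no definition of the term and no rule for a participant whose final albumin value is missing. The only related rule is in Material and methods: "If a subject declined to continue in the study, he or she was considered as a loss from follow up".

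The Results section gives the flow: "We randomized 50 participants per group and lost five in corn oil group and four in" the omega-3 group. That leaves 45 and 46. The primary result follows: "A 20% reduction in urine albumin excretion was attained in 13 participants of group 1 and 19 participants of group 2", with a Fisher p-value of 0.274 and no denominators. The first preliminary conclusion is "The primary outcome measure of the study was not attained".

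Table 1 describes everyone randomised; its gender counts add to 50 in each group. Tables 2 and 3 are headed n=45 and n=46 throughout, including their baseline columns.

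**The concern.** If intention to treat means that everyone randomised is analysed, the primary comparison should rest on 50 and 50, with a stated way of handling the nine without a final value. Two things suggested that it did not: the follow-up tables are headed with the post-loss counts, and the primary result shows no denominators at all.

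What is at stake is how the primary result is read. Someone who takes the intention-to-treat statement at face value would compute 26% vs 38%, would be unable to reproduce the p-value, and would not know that the comparison is conditional on staying in the study. No sensitivity of the result to the missing outcomes is reported.

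**Working it through.** **Inputs.** From Results: 50 randomised per group; 5 lost (corn oil) and 4 lost (omega-3); 13 responders in group 1 and 19 in group 2; Fisher p = 0.274. From Data analysis: significance level 0.05, taken as two-sided because the sidedness is not stated. No sentence says which group is which. I take group 1 as corn oil and group 2 as omega-3, and step 1 supports this.

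**Step 1: reproduce the printed p-value.** With a responders of n in one group and b of m in the other, Fisher's test uses P(X = k) = C(n, k) C(m, a + b - k) / C(n + m, a + b). The two-sided p-value sums every P(X = k) no larger than P(X = a).

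| Set | Comparison | Two-sided p |
|---|---|---|
| Not lost | 13/45 vs 19/46 | 0.2737 |
| All randomised, lost as non-responders | 13/50 vs 19/50 | 0.2837 |
| Group labels swapped | 13/46 vs 19/45 | 0.1918 |
| Mixed | 13/45 vs 19/50 | 0.390 |
| Mixed | 13/50 vs 19/46 | 0.133 |

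Only the first rounds to 0.274. On 50 and 50, other versions of the test do not give it either: one-sided Fisher 0.142, mid-p 0.246, chi-square 0.198, continuity-corrected chi-square 0.284.

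**Step 2: could other denominators give 0.274?** Of the 121 pairs with each group between 40 and 50, three round to 0.274: 45/46 (0.2737), 46/46 (0.2737) and 43/45 (0.2739). Only 45/46 matches counts given in the document, and none of the three contains all 100.

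**Step 3: cross-check on the tables.** The baseline median albumin/creatinine ratio is 604.5 (corn oil) and 365.5 (omega-3) in Table 1, but 541 and 363 in Table 3. The two tables therefore describe different sets, consistent with the lost participants having been removed from the Table 3 baseline. This shows who is in the table; it is not evidence of bias.

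**Step 4: size of the difference.** The 95% intervals use Newcombe's method. With Wilson limits (l, u) for each proportion and d = p2 - p1, the lower limit is d - sqrt[(p2 - l2)² + (u1 - p1)²] and the upper limit is d + sqrt[(u2 - p2)² + (p1 - l1)²].

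- Not lost: 13/45 = 28.9%, 19/46 = 41.3%, difference 12.4 points, 95% CI -7.1 to 30.6.
- All randomised, lost as non-responders: 13/50 = 26.0%, 19/50 = 38.0%, difference 12.0 points, 95% CI -6.2 to 29.2.

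**Step 5: bounds over the missing outcomes.** Between 0 and 5 of the lost corn oil participants and between 0 and 4 of the lost omega-3 participants could have responded, giving 6 × 5 = 30 assignments.

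| Assignment | Comparison | Difference (95% CI) | Fisher p |
|---|---|---|---|
| Most against omega-3 | 18/50 vs 19/50 | +2 points (-16.4 to 20.2) | 1.00 |
| All lost respond | 18/50 vs 23/50 | +10 points | 0.416 |
| Most in favour of omega-3 | 13/50 vs 23/50 | +20 points (1.2 to 37.0) | 0.060 |

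Fisher p is at least 0.060 in all 30.

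**The case against.** The strongest reply is that intention to treat may have been meant as analysed in the allocated group whatever the compliance. Nothing suggests that anyone changed group or was dropped for poor compliance. But the document does not say this, so the reader cannot know it; what stands is that defining the term is an acceptable alternative to relabelling.

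It can also be said that the losses are disclosed in the same section as the primary result, that the later tables carry n=45 and n=46, and that the flow figure, which is not visible in the text available here, may show the numbers analysed. That softens the harm to a careful reader. It does not turn a comparison of 91 into one of 100, and it supplies no missing-outcome rule.

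The exact pair 45/46 is inferred. Two corn oil medians in Table 3 (561.5 for the six-week albumin/creatinine ratio and 160.5 for final cholesterol) are half-integers among values that otherwise look whole. An odd count of 45 would not normally give these, so counts in some cells may be below the header. This is a further reason to print denominators, and it does not bring the nine lost back in.

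Finally, the effect is small: 12.4 becomes 12.0 points and 0.274 becomes 0.284. That is correct, and it limits the weight of the point.

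**Conclusion.** The concern holds. Given 13 and 19 responders, the printed p-value is not an all-randomised result; it is an available-case comparison that leaves out 9 of 100 participants (9%) under an intention-to-treat label that is never defined. This rests on a two-sided Fisher test and on group 1 being corn oil, which the p-value match supports.

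The primary conclusion does not reverse. By the trial's own Fisher test, no assignment of the nine missing outcomes falls below 0.05. That assurance is specific to Fisher: at the single most favourable assignment (13/50 vs 23/50) an uncorrected chi-square test gives 0.037 and the Newcombe interval excludes zero. That is an extreme case, but it shows that the estimate is less secure than the verdict on significance. The defect is a mislabelled analysis set and unreported uncertainty, which should be fixed.

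**What to change.** 1. Print the denominators with the primary result. Call 13/45 vs 19/46 an available-case (completer) analysis, or state what intention to treat means in this trial.
2. Add an all-randomised result under an explicit missing-outcome rule, labelled as chosen after the data were seen. Counting the lost as non-responders is one example: 13/50 vs 19/50, 12.0 points (95% CI -6.2 to 29.2), p = 0.284.
3. Report the bounds as sensitivity: +2 to +20 points, Fisher p from 1.00 to 0.060.
4. Table 1 already gives gender, age, body mass index and urine albumin for all 50 per group. Extend this to the remaining baseline variables, which appear only under the n=45 and n=46 headings.
5. State how many participants entered the repeated-measures models, which the document does not say. If they were limited to completers, refit them to all available data.

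The cost is a wording change and a short rerun on existing data. The p-value becomes slightly larger. The wider uncertainty comes from the bounds: the non-responder interval (29.2 + 6.2 = 35.4 points wide) is a little narrower than the completer interval (30.6 + 7.1 = 37.7). The stated conclusion on the primary outcome is unchanged.

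### Table 3 marks significance on 27 rows at an unadjusted 0.05, and after a negative primary outcome one such flag supports a hedged suggestion of benefit on arterial stiffness

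*Combined protocol and SAP*

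**What the plan says.** The Data analysis section names one primary outcome: "The main outcome of the study was set as a reduction in urine albumin excretion by 20% or more". The sample size rests on that outcome alone: "Thus, the sample size to obtain results with an α of 0.05 and a power of 0.8 was 38 participants per group". For all comparisons the only level given is "Significance level was set at 0.05". The document contains no adjustment for multiple tests, no order of testing, no ranked secondary outcomes and no statement that the other outcomes are exploratory.

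Each parameter is analysed with its own repeated-measures mixed model. Tables 2 and 3 report significance as letters in the last column. In Table 3, b means change over the intervention without a group difference, and c means change with a group difference, glossed as an omega-3 effect. No p-values appear in either table.

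The Results section reports the primary outcome, with a Fisher p-value of 0.274: "A 20% reduction in urine albumin excretion was attained in 13 participants of group 1 and 19 participants of group 2". Preliminary conclusion 1 accepts this: "The primary outcome measure of the study was not attained". Preliminary conclusion 4, which concerns arterial stiffness, then says: "The lack of increase in pulse wave velocity in group 2 may indicate that the supplement that this group received had a favorable effect".

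**The concern.** When the primary comparison is negative, readers look to the secondary rows for a benefit. If those rows are each tested at 0.05 and nothing sets their status, some group effects will appear by chance, and the document gives no rule for discounting them.

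Table 3 has two c flags. Conclusion 2 treats the triacylglycerol flag as a known pharmacological effect. That leaves pulse wave velocity as the only new favourable signal, picked out after the results from an unranked list. At stake is whether the trial may suggest a vascular benefit on one unadjusted flag whose strength the reader cannot see.

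**Working it through.** **The plan's own figures.** The Results section says: "We randomized 50 participants per group and lost five in corn oil group and four in Ω -3 group". That leaves 45 and 46 participants analysed.
- Fisher's exact test on 13/45 against 19/46 gives p = 0.274, as printed.
- With the denominators swapped (13/46 against 19/45) p = 0.192, and with all randomised (13/50 against 19/50) p = 0.284.
- The printed value therefore identifies group 1 as corn oil and group 2 as omega-3.
- The stated 38 per group is approximately recovered (36 to 37) with a 35-point difference, two-sided 0.05, 80% power, a continuity correction and an assumed control rate of 25% to 40%; the document gives no control rate.

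The primary test and the sample size are single-outcome calculations, so multiplicity does not affect them.

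**Row counts, from the tables.**
- Table 3: 27 rows. Five are flagged: b on augmentation pressure, augmentation index and glycosylated hemoglobin; c on pulse wave velocity and triacylglycerol.
- Arterial-stiffness block of Table 3: 4 rows (augmentation pressure, augmentation index, reflection magnitude, pulse wave velocity). Only pulse wave velocity carries c.

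**Chance flags.** Assume one 0.05 test per row and no true effect. For k rows, the expected number of false flags is 0.05k, which holds whatever the correlation. The chance of at least one is 1 − 0.95^k, which needs independence.

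| Family | k | Expected false flags | Chance of at least one | First Holm step, 0.05/k |
|---|---|---|---|---|
| Table 3 | 27 | 27 × 0.05 = 1.35 | 1 − 0.95^27 = 75.0% | 0.00185 |
| Arterial stiffness | 4 | 4 × 0.05 = 0.20 | 1 − 0.95^4 = 18.5% | 0.0125 |

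Setting triacylglycerol aside as a real effect changes little: 1 − 0.95^26 = 73.6%.

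**Pulse wave velocity medians, Table 3.**
- Corn oil: 9.3 to 9.7 m/s, a rise of 0.40.
- Omega-3: 9.75 to 10.1 m/s, a rise of 0.35.

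A difference between medians is not the model estimate, but these figures do not show an absence of increase in group 2. The summarizing sentence in Results says that the corn oil participants kept their pulse wave velocity while controls rose; conclusion 4 credits group 2, which is omega-3 by the Fisher check above. The two statements conflict.

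**The case against.** The strongest reply is that the document already has a hierarchy in substance. It names one main outcome, sizes the trial on it and reports its failure first. Conclusion 4 stands under a preliminary heading and is worded as a possibility. Adjusting every secondary row in a trial of 50 per group is not a universal requirement. Much of this stands: the conclusion is a suggestion rather than a firm efficacy claim, and the primary result is not in question. What remains is that no text gives the other rows exploratory status, and the hedge does not tell the reader that the signal is one of 27 rows.

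The error rates can also be challenged. Applying 0.05 to each row is inferred from the single stated level. The legend does not say whether c is one interaction test or two conditions met together; if two, the false c rate per row could be below 0.05. Many rows are correlated (weight with waist; creatinine, cystatin C and filtration rate), which would probably lower the 75%. These points make the figures indicative, not exact.

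A reader might be tempted by larger families, but the documents do not support them:
- **All 56 rows of Tables 2 and 3.** Eight of the 29 Table 2 rows are zero in every cell, and EPA and DHA are the supplement's own constituents, so that table is mainly an exposure check.
- **Six vascular rows, including carotid thickness.** Table 3 puts carotid thickness under its own heading, and conclusion 4 concerns arterial stiffness, which has four rows.

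**Conclusion.** The point holds in limited form. A single 0.05 level, no multiplicity control and no exploratory label allow an unadjusted flag to support a hedged suggestion of benefit after a negative primary outcome. Assuming one independent 0.05 test per row and no effect, 1.35 false flags are expected over Table 3, with a 75% chance of at least one; over the arterial-stiffness rows that chance is 18.5%.

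A reader might infer that the pulse wave velocity flag is a false positive or would fail adjustment. The documents do not show this. With letters in place of p-values, it cannot be known whether the flag would pass 0.0125 or 0.00185. The supportable statement is that the evidence behind conclusion 4 cannot be assessed as reported. The conflict over medians and groups is a separate weakness in the same conclusion, and a multiplicity adjustment would not resolve it.

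**What to change.** 1. State in Data analysis that the albuminuria response of 20% or more is the only confirmatory outcome, that the Table 3 tests are exploratory, and that Table 2 mainly checks exposure.
2. Say which model term or terms produce flag c. Print the group-by-time p-value for every Table 3 row, with a Holm or false-discovery-rate adjustment across the table.
3. In conclusion 4, say that the signal is one flag among 27 rows and hypothesis-generating only. Remove it if it does not survive the adjustment.
4. While rewording, reconcile conclusion 4 with the median rises of 0.40 and 0.35 m/s, and with the Results sentence that credits the corn oil group.

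The cost is a few lines of analysis on existing model output and some rewording. No new data are needed, and the primary test is unchanged. The downside is that the pulse wave velocity claim may weaken or go.

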Palmitic Acid (C16:0)	27.4 (25.2-29.9)	28.9 (27-31.1)	25.7 (23.7-28.3)	27.8 (25.5-29.2)	28.8 (26.7-30.8)	27.7 (24.8-28.9)	
Heptadecanoic Acid (C17:0)	2.4 (0.4-4.2)	3.1 (0.8-4.7)	2.3 (0.3-4.7)	1.7 (0.4-3.6)	3.1 (0.5-4.5)	2.7 (0.5-4.3)	b
Estearic Acid (C18:0)	15.6 (12.9-18.4)	15.3 (13.7-17.1)	17.5 (13.6-18.8)	16.3 (13.8-17.9)	15.6 (14-17.9)	16.9 (14.1-18.1)	
Arachidic Acid (C20:0)	0 (0-0.3)	0 (0-0.3)	0 (0-0.3)	0 (0-0.3)	0 (0-0.3)	0.2 (0-0.3)	
Eneicosanoic Acid (C21:0)	0 (0-0)	0 (0-0)	0 (0-0)	0 (0-0)	0 (0-0)	0 (0-0)	
Behenic Acid (C22:0)	0.9 (0.6-1.2)	1.1 (0.8-1.2)	0.8 (0.3-1)	1 (0.7-1.2)	1.1 (0.9-1.3)	0.9 (0.4-1.2)	
Lignoceric Acid (C24:0)	2.6 (1.4-3.4)	2.8 (2.4-3.4)	2.2 (1-3.4)	2.6 (1.3-3.3)	2.8 (2.2-3.3)	2.6 (0.8-3.3)	
Total Saturated	54.9 (50.7-58.3)	55 (51.9-57.7)	55.8 (51.7-59.8)	54.1 (49.7-58.2)	55.2 (50.1-57.8)	55.9 (52.9-62.2)	b
Miristoleic Acid (C14:1)	0 (0-0)	0 (0-0)	0 (0-0)	0 (0-0)	0 (0-0)	0 (0-0)	
Pentadecanoico Acid (C15:1)	0 (0-0)	0 (0-0)	0 (0-0)	0 (0-0)	0 (0-0)	0 (0-0)	
Palmitoleic Acid (C16:1)	0 (0-0.4)	0 (0-0.4)	0 (0-0.4)	0 (0-0.4)	0 (0-0.4)	0 (0-0.3)	
Cis 10-Heptadecanoic A Acid (C17:1)	0 (0-0)	0 (0-0)	0 (0-0)	0 (0-0)	0 (0-0)	0 (0-0)	
Oleico Acid (C18:1)	14.3 (13.3-15.7)	14.7 (13.7-15.7)	13.7 (12.1-14.5)	14.7 (13.3-15.9)	14.8 (14-16.1)	14.2 (13-15)	
Gadoleic Acid (C20:1)	0 (0-0.2)	0 (0-0.2)	0 (0-0.2)	0 (0-0.2)	0 (0-0)	0 (0-0.2)	
Erucic Acid (C22:1)	0 (0-0)	0 (0-0)	0 (0-0)	0 (0-0)	0 (0-0)	0 (0-0)	
Nervonic Acid (C24:1)	2.5 (1.5-3.1)	2.7 (2.3-3.2)	2.2 (1.7-2.7)	2.6 (1.7-3)	2.8 (2.4-3.2)	2.5 (0.9-2.8)	
Total monounsaturated	17.4 (16.2-19)	17.5 (16.9-19)	16.6 (15.3-18.5)	17.6 (16.3-19)	17.7 (17.2-19)	17.4 (15.3-18.1)	
Linoleic Acid (C18:2 n6 c)	11.8 (9.3-13.9)	12.2 (10-13.9)	11.8 (8.6-13.4)	10.9 (9.4-12.6)	11 (9.5-12.3)	9.9 (8.5-11.5)	
Gama linolenic Acid (C18:3 n6 c)	0 (0-0)	0 (0-0)	0 (0-0)	0 (0-0)	0 (0-0)	0 (0-0)	
Alfa linolenic Acid (C18:3 n-3)	0 (0-0.2)	0 (0-0)	0 (0-0.1)	0 (0-0.1)	0 (0-0)	0 (0-0.1)	
Eicosadienoico Acid (C20:2)	0 (0-0.3)	0 (0-0.3)	0.1 (0-0.3)	0 (0-0.3)	0 (0-0.3)	0 (0-0.2)	
Table 2 continuation							
	Corn oil group (n=45)			Ω-3 Group (n=46)			p ¹
	Basal	Six weeks	Basal	Six weeks	Basal	Six weeks	

Dihomo gamalinolenic Acid (C20:3 n-6)	1.5 (1.1-1.9)	1.4 (1.1-1.7)	1.4 (1-1.9)	1.3 (0.8-1.9)	1.1 (0.8-1.5)	1.2 (0.7-1.6)	
Cis-11-14 icosatrienoico Acid (C20:3 n-3)	0 (0-0)	0 (0-0)	0 (0-0)	0 (0-0)	0 (0-0)	0 (0-0)	
Arachidonic Acid (C20:4 n-6)	9.4 (6.1-12.5)	10.1 (6.2-12.1)	9.1 (6.4-12.6)	8.9 (5.5-11.7)	8.8 (6.6-11.1)	8.1 (5.1-10)	

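### Conclusion 4's pulse wave velocity benefit does not match Table 3, and the four rows coded as omega-3 effects carry no between-group estimate or confidence interval

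*Combined protocol and SAP*

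**What the plan says.** - **Allocation (Material and methods).** Two groups were formed, "balancing by gender, age, body mass index and urine albumin excretion expressed per mg of creatinine". The comparator is defined by "Placebo supplement: Contained corn oil".
- **Baseline (Results, Table 1).** Table 1 shows those same four factors for 50 participants per group. The text concludes: "No differences between groups were observed, therefore the premises of randomization were correctly attained".
- **Fatty acids (Results, Table 2).** "Patients receiving the active supplement had significant increases in eicosapentanoic and docosahexanoic fatty acid levels". Table 2 gives medians, quartiles and a letter code.
- **Pulse wave velocity.** The summarising paragraph of Results says "participants receiving corn oil maintained their pulse wave velocity during the follow up while controls experienced an increase in this parameter". Conclusion 4 begins "The lack of increase in pulse wave velocity in group 2 may indicate that the supplement" and goes on to claim a favourable effect on arterial stiffness.
- **Codes.** Data analysis names a mixed linear regression model for repeated measures. In Tables 2 and 3 its only printed output is a letter. Code c, read as an omega-3 effect, stands on four rows: EPA, DHA, triacylglycerol and pulse wave velocity.

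**The concern.** The primary outcome was null, so the secondary findings carry the positive message, and conclusion 4 is the one arterial benefit claimed. Its premise, that velocity did not rise in group 2, does not match the medians in Table 3. The summarising paragraph attaches the benefit to the other product. A reader cannot tell which arm is meant or how large the effect is.

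The same gap affects all four rows coded c. Where arms differ at baseline, the final difference and the difference in change are different numbers, and a letter gives neither. EPA and DHA matter most here, because they are the evidence that the supplement reached its target.

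The randomisation sentence adds to this. Similarity on factors that the allocation was built to balance says little about variables that it did not balance.

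**Working it through.** **1. Which arm is group 2?** Results gives 13 responders in group 1, 19 in group 2, Fisher p = 0.274. Losses of five (corn oil) and four (omega-3) leave 45 and 46, the sizes in Tables 2 and 3.

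| Assignment | Fisher p |
|---|---|
| 13/45 v 19/46 (group 2 = omega-3) | 0.274 |
| 13/46 v 19/45 (group 2 = corn oil) | 0.192 |
| 13/50 v 19/50 | 0.284 |

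Only the first reproduces the printed figure, so group 2 appears to be omega-3.

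**2. Pulse wave velocity in Table 3 (m/s, median and quartiles).**

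| Arm | Basal | Six weeks | Final | Change in median, basal to final |
|---|---|---|---|---|
| Corn oil | 9.3 (8.5-10.7) | 9.7 (8.3-11) | 9.7 (8.3-11.2) | 9.7 - 9.3 = +0.40 |
| Omega-3 | 9.75 (8.1-10.6) | 10 (7.6-10.8) | 10.1 (8-10.9) | 10.1 - 9.75 = +0.35 |

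The changes differ by 0.35 - 0.40 = -0.05 at the end. At six weeks they differ by (10 - 9.75) - (9.7 - 9.3) = -0.15. Neither arm shows a flat median, so the mismatch with conclusion 4 does not depend on step 1.

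**3. How far can step 2 be pushed?** A difference between group medians is not a median of individual changes. In simulated normal data (SD 1.7 and 2.1, n = 45 and 46, within-person correlation assumed 0.7 to 0.98), the error in recovering the between-group change had an SD of about 0.22 to 0.38 m/s from medians, and about 0.13 to 0.20 from averaged quartiles. That is several times 0.05, so the printed figures can neither confirm nor refute the model.

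**4. EPA and DHA (Table 2, mg/100 mg of total fatty acids).** Both rows lie under "Table 2 continuation", where the header repeats basal and six weeks. The column order of the first part is assumed.

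| | Basal gap in medians | Final gap in medians | Basal/final |
|---|---|---|---|
| EPA | 1.3 - 0.4 = 0.9 | 2.6 - 0.5 = 2.1 | 43% |
| DHA | 2.7 - 1.9 = 0.8 | 2.8 - 1.6 = 1.2 | 67% |

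With means taken as (Q1 + median + Q3)/3, the shares are 1.2/1.9 = 63% and 0.8/1.4 = 57%.

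A rough baseline-adjusted difference is: final gap - r x (final SD/basal SD) x basal gap, with SD = IQR/1.349. The basal-to-final correlation r is not in the document and is assumed to be 0.3 to 0.9. For example, DHA on means, with an SD ratio of 1.076, gives 1.4 - 0.9 x 1.076 x 0.8 = 0.63 at r = 0.9. Over both estimators:

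| Row | Adjusted difference, week 12 | Approximate 95% limits |
|---|---|---|
| EPA | 0.9 to 1.9 | exclude zero (lowest 0.65) |
| DHA | 0.4 to 1.1 | exclude zero (lowest 0.09) |
| Triacylglycerol (mg/dl) | -36 to -45 | exclude zero (highest -0.8) |
| Pulse wave velocity (m/s) | -0.10 to +0.23 | include zero throughout |

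These limits leave out the reconstruction error of step 3 and are indicative only.

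**5. Basal gaps outside Table 1 (45 v 46).** Differences in means rebuilt from quartiles, Welch test:

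- Weight (medians 76.4 v 90.4 kg): 11.0 kg (95% CI 4.3 to 17.8), p = 0.0017
- EPA: 1.2 (0.61 to 1.79), p = 0.00016
- DHA: 0.8 (0.31 to 1.29), p = 0.0018

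These rows were picked from 29 + 27 = 56. At 0.05/56 = 0.0009 only EPA passes. It does so by this method only: the median-based p is 0.015, and a Fisher test on counts implied by the quartiles gives 0.031.

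**The case against.** **The randomisation sentence may be true as meant.** The premises can be read as the four balancing factors, and the preceding sentence refers to Table 1. This largely stands, so narrowing the sentence is a matter of wording. A reader might infer from the weight, EPA and DHA gaps that randomisation failed. The documents do not support that. The rows were selected after the fact, EPA is skewed (corn oil lower quartile 0), and the values cover the 91 participants not lost rather than all 100 randomised. Weight is also partly reflected in the printed BMI medians, 31 v 33.5.

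**The model may be right about pulse wave velocity.** It uses paired data and all three visits. This stands: step 2 shows that the conclusion disagrees with the medians, not that code c is false.

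**The summarising paragraph may contain only an arm-name slip.** That is plausible given step 1. Correcting the name still leaves an omega-3 median that rose by 0.35 m/s.

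**The model may already separate a constant gap from a change.** Weight has a stable gap and carries no code, which fits. A reader might infer that the EPA and DHA effects are baseline artefacts; step 4 points the other way. What is missing is their size.

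**The Table 2 labels may be a PDF-reading fault.** In the text as read, c is defined twice, and the code for a group difference without intervention effect is b in Table 2 but a in Table 3. This cannot be held against the plan without the source file.

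**Conclusion.** Conclusion 4 is wrong as written. It rests on a lack of increase that Table 3 does not show in either arm (+0.40 and +0.35 m/s in medians), and the summarising paragraph credits the placebo oil. Whether a pulse wave velocity effect exists cannot be settled from the printed quartiles. The claim is unsupported as presented, not refuted.

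Secondarily, none of the four rows coded c has a between-group estimate or interval. For EPA and DHA, about 43% to 67% of the final gap appears to have been present at baseline, depending on row and estimator and on the assumed column order. Effects on EPA, DHA and triacylglycerol probably persist after adjustment, but their size cannot be read from a letter. Balance is supported only for the four allocation factors; the other basal gaps may be chance.

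The null primary result is untouched.

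**What to change.** 1. **Estimate the four rows.** Report between-group differences with 95% intervals at weeks 6 and 12 from the repeated-measures mixed model, with group, visit, group-by-visit and the four balancing factors. Either use weeks 6 and 12 as the response with the basal value as covariate, or keep the basal visit in the response with a common baseline mean across groups. Do not do both, since that would use baseline twice. Add a transformed or rank-based check for EPA, and label these analyses post hoc.
2. **Reword conclusion 4 and the summarising paragraph.** Name the arm, and make both agree with Table 3 and the new estimate. If the pulse wave velocity interval includes zero, withdraw the claim of a favourable effect.
3. **Narrow the randomisation sentence** to the balancing factors, and mention the basal gaps in weight, EPA and DHA.
4. **Check the Table 2 continuation header and footnote letters** against the source file, and correct them only if the fault is there.

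The cost is a small reanalysis of existing data and some text edits. The pulse wave velocity finding may be lost, and the stated EPA and DHA effects may look smaller than the final gaps suggest.
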